3.7.2.4. Examination of Subgroups

The following subgroup category will be examined for the primary efficacy endpoint:

- Male vs. Female

- Black vs. non-Black
- US vs. Non-US
- Prior olanzapine exposure (subjects on olanzapine at Visit 1 vs. subjects not on olanzapine at Visit 1)
- Baseline PANSS (≥ 70 vs. < 70)
- Baseline alcohol consumption risk category (medium, high or very high risk vs. abstinence or low risk)
- Baseline AUD severity (severe vs. mild or moderate)
- Baseline number of prior hospitalizations or ER visits for the underlying disease in the last 12 months (≥ 1 vs. 0)

For each subgroup category, the Cox proportional hazards model will be used to obtain an estimate of the hazard ratio of the ALKS 3831 group to the olanzapine group. The model will include treatment group, subgroup, and treatment by subgroup interaction as factors and adjust for the relevant baseline covariates/factors when appropriate.

3.7.3. Secondary Efficacy Endpoints

Secondary efficacy endpoints include:

- The rate and number of EEDS
- Proportion of subjects with at least 1 level decrease in World Health Organization (WHO) drinking risk level from baseline to week 24 of the double-blind treatment (study week 27)

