5.2.1. Clinical Studies

In the clinical studies of samidorphan to date, 469 subjects have received samidorphan orally (1-55.7 mg) or sublingually (1-16 mg) for up to 12 weeks. Commonly reported AEs observed across all studies included nausea, fatigue, and somnolence. Other AEs observed in these studies included dry mouth, vomiting, constipation, decreased appetite, headache, dizziness, and anorexia. Overall, no trends or clinically meaningful changes have been observed in clinical

laboratory analytes, vital sign parameters, or electrocardiogram (ECG) data. No deaths have occurred in these studies.

Samidorphan has been shown to block opioid agonist effects in opioid-experienced adults and decrease alcohol consumption in alcohol-dependent adults. In opioid-experienced adults, samidorphan blocked both the subjective (eg, Drug Liking measured with a visual analog scale [VAS]) and physiological effects (eg, pupil constriction measured with pupillometry) of the opioid agonists remifentanyl (Study ALK33-004) and buprenorphine (Study ALK33-008). In adults with alcohol dependence (N=410), samidorphan (1, 2.5, or 10 mg) was associated with a reduction in drinking behavior (Study ALK33-005) compared with placebo; the largest reduction was seen with the highest samidorphan dose administered in this study (10 mg).

In addition to the reduction of alcohol drinking, samidorphan may attenuate weight gain associated with olanzapine. A Phase 1 proof-of-concept study has been conducted in healthy adults (ALK33-301) to determine the safety, tolerability, and efficacy of samidorphan when taken with olanzapine to mitigate olanzapine-related weight gain. In this study, significantly less weight gain was seen in the ALKS 3831 treatment arm than in the olanzapine plus placebo arm. A Phase 2 study, ALK3831-302, is currently underway to evaluate (as a secondary outcome) attenuation of weight gain by ALKS 3831 compared with olanzapine plus placebo in subjects with schizophrenia.

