9. TREATMENT OF SUBJECTS

9.1. Study Drug Dose and Administration

Study drugs include samidorphan and matching placebo tablets, and olanzapine tablets, all for oral administration.

For all subjects, open-label samidorphan 10 mg will be taken once daily for 2 weeks prior to randomization. For subjects in the double-blind treatment period, samidorphan 10 mg (or placebo) will be taken once daily for up to 15 months.

For all subjects, the dose of olanzapine will be taken once daily (to be taken at the same time as samidorphan/placebo) at an individualized dose level. Olanzapine initiation, including transition from another antipsychotic (as applicable), is a highly individualized process. Formalizing the potential clinical scenarios may pose undue burden and/or risk to subjects. Clinical judgment is essential, and for this reason, the details of this process are left to the discretion of the treating physician, who will follow current clinical practice.

All subjects will be administered olanzapine for 11 to 17 months as part of this clinical trial.

ALKS 3831 should be taken as close to bedtime as possible. Subjects should not drive or operate heavy machinery until they know how ALKS 3831 will affect them.

After Visit 5, the dose level of olanzapine will be fixed, and an increase in dose level above the dose set at Visit 5 prior to randomization may cause the subject to be discontinued. The olanzapine dose level may be decreased at any time if the PI considers it medically beneficial to the subject, such as when a subject has stable psychiatric symptoms with side effects that may be reduced if the olanzapine dose level is decreased. If the PI decreases the dose level after randomization, only an increase above the dose level at randomization will be considered an EEDS.

At study drug dispensation visits, all subjects will receive blister cards containing samidorphan or placebo for self-administration; subjects will also receive olanzapine in separate packaging. Subjects will be instructed to take 1 tablet per day from the blister card in addition to their olanzapine tablet(s) once daily in the evening or at bedtime. The subject will take the final samidorphan/placebo dose the night before the final visit of the double-blind treatment period. Olanzapine dosing will continue uninterrupted through the end of the study. Any subject who prematurely discontinues from the study will be asked to return to the clinic for an ET visit and 2 safety follow-up visits.

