3. DATA ANALYSIS

3.1. General Statistical Methodology

The baseline for each efficacy and safety parameter in a period is defined as the last assessment made on or before the first dose of study drug in that period. That is, baseline for open-label Olanzapine and ALKS 3831 period is defined as the last non-missing observation on or before the first dose of study drug for the open-label period at Visit 2 and 6, respectively; baseline for double-blind period is defined as the last non-missing observation on or before the date of the first dose of study drug for double-blind period at Visit 8.

Unless specified otherwise, the efficacy parameters will be summarized for the double-blind period and the safety parameters will be summarized for the open-label, double-blind and safety follow-up periods.

Continuous variables will be summarized by number of subjects and mean, SD, median, minimum, and maximum values. Categorical variables will be summarized by number and percentage of subjects.

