3.2.4. Efficacy Population

The intent-to-treat (ITT) population is the same as the safety population.

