3.7.3.1.3. Additional Analysis on the Rate and Number of EEDS

Since the EEDS consists of a series of individual criteria, number and percent of subjects who met each individual criterion will be provided. The treatment groups will be compared by the logistic regression model adjusting for the baseline PANSS total score and drinking status.

In addition, the duration of IAC confirmed hospitalizations related to the underlying disease will be summarized by treatment group.

3.7.3.2. Proportion of Subjects with at least 1 Level Decrease in World Health Organization (WHO) Drinking Risk Level from Baseline to Week 24 of Double-blind Treatment (Study Week 27)

The alcohol consumption per day at each visit will be calculated based on the number of drinks per day as follows.

$$\text{Alcohol consumption per day} = \frac{\text{total number of drinks} \times 14 \text{ gram}}{\text{total number of days}}$$

The risk of the alcohol consumption will be categorized based on the alcohol consumption per day using the criteria in Table 1. Proportion of subjects with at least 1 level decrease in World Health Organization (WHO) drinking risk level³ from baseline to week 24 of double-blind treatment (study week 27) will be compared between two treatment groups using the logistic regression model based on LOCF (last observation carried forward) imputation for the missing data, that is, the last observed non-missing post-baseline value will be carried forward for the missing post baseline assessments. The model will include the treatment group as factor and adjust for the baseline PANSS total score and drinking status.

Table 1: Criteria for risk of alcohol consumption on a single drinking day

Risk Category	Males	Females
Abstinence	0 g	0 g
Low Risk	1 to 40 g	1 to 20 g
Medium Risk	41 to 60 g	21 to 40 g
High Risk	61 to 100 g	41 to 60 g
Very High Risk	≥ 101 g	≥ 61 g

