3.7.4.6.1. Categorical endpoints for the Complete Response Profile of Drinking

The following categorical endpoints for the complete response profile of drinking during the double-blind treatment period will be analyzed using a logistic regression model.

- Proportion of subjects with at least 1 level decrease in World Health Organization (WHO) drinking risk level from baseline by visit
- Proportion of subjects with at least 2 levels decrease in World Health Organization (WHO) drinking risk level from baseline by visit
- Proportion of subjects abstinent from heavy drinking days from randomization through week 24 of the double-blind treatment period (study week 27)
- Proportion of subjects abstinent from heavy drinking days by visit
- Proportion of subjects abstinent from drinking days by visit

The model will include treatment as factor and adjust for baseline PANSS and drinking status. LOCF imputation will be used for the by-visit summary.

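### With a Visit 8 baseline, the WHO drinking-level responder endpoints count as failures subjects already too low on the scale to respond, which dilutes the result by an amount the documents leave open

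*SAP*

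**What the plan says.** SAP 3.7.3 names as secondary the "Proportion of subjects with at least 1 level decrease in World Health Organization (WHO) drinking risk level from baseline to week 24" of double-blind treatment. SAP 3.7.4.6.1 adds, among the other efficacy endpoints, the "Proportion of subjects with at least 2 levels decrease in World Health Organization (WHO) drinking risk level from baseline by visit". SAP Table 1 has five levels: abstinence (0 g), low, medium, high and very high.

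Neither endpoint limits the denominator by baseline level. The efficacy population is everyone randomized and dosed: "The intent-to-treat (ITT) population is the same as the safety population" (SAP 3.2.4).

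On baseline, SAP 3.1 states that "baseline for double-blind period is defined as the last non-missing observation on or before the date of the first dose of study drug" in that period, at Visit 8. Before that visit, "open-label samidorphan 10 mg will be taken once daily for 2 weeks prior to randomization" by all subjects (Protocol 9.1). The randomization criteria in Protocol 7.3 cover PANSS, CGI-S and an opiate screen, but not drinking.

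On the model, SAP 3.7.3.2 specifies logistic regression with LOCF: "The model will include the treatment group as factor and adjust for the baseline PANSS total score and drinking status". SAP 3.7.4.6.1 uses the same adjustment. Drinking status is not defined in either place.

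**The concern.** A responder endpoint should count subjects for whom response is possible. Someone at 0 g cannot move down a level, and someone at abstinence or low risk cannot move down two. As written, these subjects are failures in both arms whatever treatment does, so they carry no information on the treatment effect.

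Such subjects can plausibly exist at Visit 8. If the TLFB is completed at both Visits 6 and 8, the Visit 8 value describes the open-label samidorphan fortnight (Protocol 8.3.12 and Tables 1 and 2). Protocol 5.2.1 credits samidorphan with reducing drinking, most at the dose used here.

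At stake are the readability and power of one of the two secondary endpoints and of one descriptive companion. The SAP already applies the natural rule elsewhere: for laboratory and ECG abnormalities (3.8.3 and 3.8.5), only subjects without the abnormality at baseline enter the percentage.

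**Working it through.** **The plan's own figure.** No power is stated for the WHO endpoints. The only sizing (SAP 2) is for the primary endpoint, and it reproduces. The hazard ratio is ln(0.85)/ln(0.70) = 0.456. With 70 events, power = Φ(√70 × |ln 0.456|/2 − 1.96) = Φ(3.29 − 1.96) = 91%, against the stated 90%. This point does not touch it; I take only the 135 per arm.

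**Who cannot respond, by endpoint and baseline visit.** Inclusion 11 (Protocol 7.1) requires at least 10 drinking days in 30, at least 2 of them heavy (5 drinks for men, 4 for women). SAP 3.7.3.2 uses 14 g per drink.
- Men, minimum: (8×1 + 2×5) × 14/30 = 8.4 g/day.
- Women, minimum: (8×1 + 2×4) × 14/30 = 7.5 g/day.

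Both fall in the low-risk band (1 to 40 g and 1 to 20 g). At screening nobody is abstinent, so everyone could fall one level, but some could never fall two. The 1-level problem therefore arises only with the Visit 8 baseline. The 2-level problem exists at either visit.

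**Dilution.** Let f be the share unable to respond, and p1 and p0 the response rates among those able. The all-ITT rates are p1(1−f) and p0(1−f), so the risk difference shrinks by exactly the factor (1−f). Power is Φ(difference/SE − 1.96) with the unpooled SE, n = 135 per arm for all ITT and 135(1−f) for the restricted set. The values of f, p1 and p0 are assumptions.

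Worked case, 60% vs 45% and f = 20%:
- All ITT: rates 48% and 36%. OR = (0.48/0.52)/(0.36/0.64) = 1.64. SE = √((0.2496 + 0.2304)/135) = 0.0596. Power = Φ(2.01 − 1.96) = 52%.
- Able to respond (n = 108): OR = (0.60/0.40)/(0.45/0.55) = 1.83. SE = √((0.2400 + 0.2475)/108) = 0.0672. Power = Φ(2.23 − 1.96) = 61%.

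| Response if able | f | OR, all ITT | OR, able | Power, all ITT | Power, able |
|---|---|---|---|---|---|
| 60% vs 45% | 10% | 1.72 | 1.83 | 61% | 66% |
| 60% vs 45% | 20% | 1.64 | 1.83 | 52% | 61% |
| 60% vs 45% | 30% | 1.57 | 1.83 | 44% | 55% |
| 60% vs 45% | 40% | 1.52 | 1.83 | 36% | 49% |
| 45% vs 30% | 20% | 1.78 | 1.91 | 58% | 63% |
| 35% vs 20% | 20% | 2.04 | 2.15 | 67% | 71% |
| 30% vs 15% | 20% | 2.32 | 2.43 | 74% | 77% |
| 30% vs 15% | 10% | 2.37 | 2.43 | 80% | 81% |

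For the 2-level endpoint f can be larger. At f = 60% with 60% vs 45%, the rates are 24% and 18%. Power is Φ(0.06/0.0494 − 1.96) = 23% in all ITT, against Φ(0.15/0.0950 − 1.96) = 35% in the 54 per arm able to respond.

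**Role of the covariate.** If drinking status is the five-level WHO category, the abstinent cell has no responders. Its coefficient runs to minus infinity and the cell drops out of the likelihood for treatment. In 2,000 simulated trials (20% abstinent, 60% vs 45%) the treatment log odds ratio matched the eligible-only fit to within 3×10⁻¹², with median OR 1.87 and power 60.8% in both. With a two-group or continuous coding the dilution stays: OR about 1.7 and power about 54%. For the 2-level endpoint, the two-group split in SAP 3.7.2.4 (medium or above against abstinence or low) itself makes a cell with no possible responders.

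**The case against.** Keeping every randomized subject is a legitimate ITT choice. The proportion of all randomized subjects who improve is a valid quantity, and the dilution runs toward the null, so it does not favour the product. Other drinking measures in SAP 3.7.4.6, such as percent heavy drinking days, have no responder floor of this kind. Table shells and programming specifications are separate documents and might hold a denominator rule. All of this stands. It limits the point to efficiency and clarity on a secondary endpoint; it does not remove it.

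Three stronger readings are tempting, and the documents do not support them.
- A reader might infer that the fault lies in the responder definition and holds from any baseline visit. That is true for the 2-level endpoint only, because inclusion 11 rules out abstinence at screening.
- A reader might infer that the plan suffers both a diluted odds ratio and a broken model. For the 1-level endpoint these are alternatives: the coding that creates the empty cell also returns the undiluted treatment estimate. In simulation, outright fitting failures occurred with one algorithm (11 to 12% of 1-level trials) and not with another, so they are not inherent to the data.
- A reader might infer that the subgroup in SAP 3.7.2.4, "Baseline alcohol consumption risk category (medium, high or very high risk vs. abstinence or low risk", shows that many abstinent subjects are expected. It only completes a split of the five levels and could consist almost wholly of low-risk subjects.

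**Conclusion.** The point holds for the Visit 8 baseline that the SAP specifies. Any subject abstinent then is a certain failure on the 1-level endpoint, and any subject abstinent or at low risk is a certain failure on the 2-level endpoint. Raw proportions and the risk difference are diluted by that share under any covariate coding. The odds ratio and power are also weakened unless drinking status enters as the WHO category; then only the floor-cell coefficient cannot be estimated.

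The size cannot be fixed from the documents. At 20% abstinent and a 15-point difference among subjects able to respond, the unadjusted power loss runs from about 9 points (60% vs 45%) to about 3 points (30% vs 15%). These figures omit the planned adjustment. The primary endpoint and its sample size are unaffected. The change is worth making because it is cheap, not because the loss is known to be large.

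**What to change.** In SAP 3.7.3.2 and 3.7.4.6.1:
- Analyse the 1-level endpoint in ITT subjects whose Visit 8 baseline is at least low risk, and the 2-level endpoint in those at least at medium risk.
- Report the number excluded per arm, and keep the all-ITT version as supportive.
- Define drinking status in a coding that leaves no cell without possible responders, for example baseline grams per day as a continuous covariate.

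The restriction uses a value fixed before randomized treatment starts, so the randomized comparison is preserved. The cost is a few sentences, written before unblinding. The downside is a smaller denominator and higher-looking percentages, which must be labelled as among subjects able to respond.

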3.7.3.1. Rate and Number of EEDS

3.7.3.1.1. Primary Analysis on the Rate and Number of EEDS

Considering EEDS as recurrent events, an Andersen-Gill mean/rate intensity model will be employed to analyze the time-to-recurrent EEDS. This model will allow for an arbitrary dependence structure of the recurrent events within the same subject by using a robust “sandwich” estimate of the covariance matrix. The model will also adjust for the baseline PANSS total score and drinking status. The estimated hazard ratio (and 95% confidence interval) of the ALKS 3831 group to the olanzapine group will be calculated under the Anderson-Gill mean/rate intensity model.

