During the double-blind treatment period, subjects will complete an outpatient visit every 2 weeks. As indicated in the schedule of assessments (see [Table 1](#), [Table 2](#), and [Table 3](#)), at some of these visits, subjects will complete a number of clinical assessments, receive a 15-minute counseling intervention (see [Section 8.3.26](#)), and will receive a 2-week study drug supply (including extra medication in case the subject does not return to the study site on the scheduled day; see [Section 10](#)). Other visits will be only drug dispensing visits during which subjects will only receive a 2-week study drug supply. No clinical assessments will be completed at drug dispensing visits.

Subjects randomized to double-blind treatment will be followed for a minimum of 9 months and a maximum of 15 months. After the end of the double-blind treatment period, subjects will complete a 3-week safety follow-up period. The study will be stopped when the last subject randomized is scheduled to complete Visit 26. When the last subject is randomized, all subjects currently participating in the study will be informed of the target completion date of the study period. After the last double-blind treatment period visit, subjects will proceed to the safety follow-up period.

The duration of the double-blind period will be between 9 and 15 months, depending on when the study is stopped. The target completion date will be based on the number of subjects randomized with enrollment ending when approximately 270 subjects have been randomized. After the last subject is randomized, the end date of the study will be set to occur approximately 9 months later and subjects will be informed of the target completion date. Final

samidorphan/placebo dosing for these subjects will take place the night before their final visit of the double-blind treatment period. A subject who is prematurely discontinued from the study will proceed as described in [Section 7.4](#).

After a subject completes an ET Visit and/or the safety-follow-up period, follow-up clinical care may be provided for up to 3 months if the PI determines that it is medically indicated. This care may include payments for medication and up to 3 clinic (outpatient) visits.

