If no withdrawal criteria have been met, subjects experiencing an EEDS (except event #7) may continue in the study at the discretion of the PI.

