2. SAMPLE SIZE CONSIDERATION

The sample size calculation is based on the detection of hazard ratio for the first event of exacerbation of disease symptoms (EEDS) during the double-blind treatment period.

Based on the previous clinical studies with olanzapine and clinical judgment, the 9-month cumulative proportion of subjects experiencing an event of exacerbation of disease symptoms (EEDS) will be 15% and 30% for the ALKS 3831 group and olanzapine plus placebo group, respectively. Assuming an exponential distribution of survival time, and a 2-sided test at $\alpha=0.05$, a total of 70 EEDS will be required for approximately 90% power to detect a hazard ratio of 0.45 between ALKS 3831 and olanzapine plus placebo with a randomization allocation ratio of 1:1 (ALKS 3831:olanzapine plus placebo). Approximately 270 subjects (135 subjects per treatment group) will need to be randomized at Visit 8 to observe 70 total EEDS.

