3.7.2.2. Sensitivity Analysis of the Primary Efficacy Endpoint

As sensitivity analysis, if the first adjudicated EEDS only satisfies the discontinuation criterion, (either satisfies 7b or 7c criteria in EEDS definition, or if IAC doesn't specify a criterion), it will be censored at the last EEDS assessment date. Analysis will be the same as the primary analysis of EEDS.

Additional sensitivity analysis will be performed to assess the potential impact of informative censoring. 10%, 20% and 30% of subjects who discontinued from the study without any EEDS will be randomly assigned as having EEDS one day after the discontinuation. Twenty imputations will be carried out. The generated datasets will be analyzed similarly as the primary analysis using the cox proportional hazard model. Rubin's rule will be used to combine the treatment effect estimates and standard errors across imputations.

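### The recurrent-EEDS rate counts a confirmed criterion 7 discontinuation as one more recurrent event, and no recurrent-event or rate analysis separates it from exacerbations

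*SAP*

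**What the plan says.** Protocol 11.1 and SAP 3.7.2 define an EEDS by eight criteria. Criterion 7 is discontinuation for lack of efficacy (7a), loss to follow-up (7b) or withdrawal by the subject (7c). An event counts only if the IAC confirms that it is related to worsening of disease.

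Protocol 11.1 adds that, if no withdrawal criterion is met, "subjects experiencing an EEDS (except event #7) may continue in the study at the discretion of the PI".

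The rate and number of EEDS is the first secondary endpoint (SAP 3.7.3). Its primary analysis, SAP 3.7.3.1.1, reads: "Considering EEDS as recurrent events, an Andersen-Gill mean/rate intensity model will be employed to analyze the time-to-recurrent EEDS". A robust variance covers dependence within subjects. The sensitivity analysis in 3.7.3.1.2 fits a negative binomial or Poisson model to the same events, with time to the last EEDS assessment visit as the offset. SAP 3.7.4.2 applies both models to psychosocial events, which include all the EEDS criteria (Protocol 11.2).

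For time to first EEDS, SAP 3.7.2.2 has a separate rule. If the first EEDS meets only 7b or 7c, or the IAC names no criterion, "it will be censored at the last EEDS assessment date".

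**The concern.** A rate model treats its events as repeatable. Criterion 7 is not: it happens once, and no further EEDS can be observed after it. The robust variance allows for correlated events but does not change what is counted. The estimated ratio therefore blends an exacerbation ratio with a discontinuation ratio.

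The rate endpoint is more exposed to this than the primary endpoint. A withdrawal after an earlier EEDS has no effect on time to first EEDS, but it adds an event to the recurrent count. The SAP nevertheless provides the 7b/7c check only for the first event.

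At stake is how the result is read. A ratio below 1 could reflect fewer exacerbations, fewer confirmed discontinuations, or both. A ratio near 1 could hide a real difference in exacerbations.

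**Working it through.** **The plan's own figure.** SAP 2 states that "a total of 70 EEDS will be required for approximately 90% power to detect a hazard ratio of 0.45", with 9-month proportions that "will be 15% and 30% for the ALKS 3831 group and olanzapine plus placebo group, respectively".

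- Implied ratio: ln(0.85)/ln(0.70) = 0.456.
- Schoenfeld events at two-sided 0.05 and 90% power: 4(1.960 + 1.282)²/(ln HR)², which gives 66 at HR 0.45 and 69 at 0.456. With 70 events at HR 0.45 the power is 91.6%.

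The figure reproduces. It concerns the first EEDS; the plan states none for the recurrent endpoint.

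**What pooling does.** Let s be the share of control-arm EEDS that are criterion 7, rE the rate ratio for all other EEDS, and r7 the rate ratio for criterion 7. With constant rates, the pooled ratio is

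R = (1 − s)·rE + s·r7.

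If r7 = rE, then R = rE and pooling is harmless. Otherwise R is pulled towards r7.

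**Illustration that respects the design.** The 15% and 30% are proportions with any EEDS, so they already include criterion 7. Criterion 7 must therefore be taken out of them, not added on top. The cumulative rates over 9 months are:

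- ALKS 3831: −ln(0.85) = 0.1625 (0.0181 per month).
- Olanzapine plus placebo: −ln(0.70) = 0.3567 (0.0396 per month).

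Assume a confirmed criterion 7 risk p, equal in both arms by 9 months, with cumulative rate w = −ln(1 − p). The ratio for the remaining EEDS is (0.1625 − w)/(0.3567 − w).

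| p (assumed) | w | Share of control EEDS, w/0.3567 | Share of ALKS 3831 EEDS, w/0.1625 | Ratio for remaining EEDS |
|---|---|---|---|---|
| 2.5% | 0.0253 | 7% | 16% | 0.1372/0.3314 = 0.41 |
| 5% | 0.0513 | 14% | 32% | 0.1112/0.3054 = 0.36 |
| 10% | 0.1054 | 30% | 65% | 0.0572/0.2513 = 0.23 |

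The pooled ratio is 0.456 in every row. As a check on the 5% row: 0.856 × 0.364 + 0.144 × 1 = 0.456.

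**Where criterion 7 is and is not separated.**

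- SAP 3.7.2.2: removes 7b/7c-only events, for the first EEDS only.
- SAP 3.7.3.1.3: compares the arms on the proportion meeting each criterion. It uses no exposure time, although "Subjects randomized to double-blind treatment will be followed for a minimum of 9 months and a maximum of 15 months", and it ignores repeat events.
- SAP 3.3 and 3.7.5: give reasons for discontinuation by arm and time to discontinuation of study drug.
- SAP 3.7.3.1.1, 3.7.3.1.2 and 3.7.4.2: no version without criterion 7.

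SAP 3.7.3.1.1 states no at-risk rule. That follow-up ends at a criterion 7 event is inferred from Protocol 11.1 and from the offset in 3.7.3.1.2.

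**The case against.** Counting a disease-related withdrawal as a treatment failure is a legitimate composite choice. The IAC filter is meant to remove withdrawals unrelated to worsening, and adverse events are a separate discontinuation reason (Protocol 7.4). These points stand, and they are why the planned models should remain.

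A reader might infer more than the documents support, in three ways:

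- **That the SAP never separates criterion 7.** It does so in 3.7.3.1.3, and for the first event in 3.7.2.2. What is missing is a rate.
- **That dropout for convenience or tolerability will drive the result.** The definition requires confirmed relation to worsening. How the IAC rules on 7b and 7c is left to its charter, which is not part of these documents.
- **That a true exacerbation ratio of 0.45 is diluted by adding dropout to it.** The 0.45 is the composite ratio. A 20% dropout by 9 months, fully confirmed, would mean −ln(0.80)/9 = 0.0248 per month, more than the whole ALKS 3831 EEDS rate of 0.0181.

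Excluding criterion 7 also has a cost. Withdrawal becomes censoring, which leaves some bias if subjects at higher relapse risk withdraw more. Removing 7a is the most debatable step, since lack of efficacy is close to the outcome itself.

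**Conclusion.** The point holds for the rate analyses. Confirmed criterion 7 discontinuations enter them as recurrent events, and neither the Andersen-Gill model nor its sensitivity analysis shows the rate without them. The primary endpoint is not affected.

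The size cannot be derived from the documents. The 0.41, 0.36 and 0.23 rest on constant rates, no variation in risk between subjects, equal criterion 7 risk in both arms, and assumed values of that risk. They show that the exacerbation ratio can differ noticeably from the pooled one; they do not predict by how much. With equal criterion 7 risk and fewer exacerbations on ALKS 3831, pooling understates the benefit. With unequal risk it can move the ratio either way. This is an inexpensive improvement, not a flaw that invalidates the endpoint.

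**What to change.** Keep the planned models and make these additions:

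- In SAP 3.7.3.1.2, and through it 3.7.4.2, add a sensitivity analysis parallel to 3.7.2.2. Refit the Andersen-Gill and negative binomial models without events that meet only 7b or 7c, or for which the IAC names no criterion, ending follow-up at the last EEDS assessment. A second version that also excludes 7a is optional.
- In SAP 3.7.3.1.1, state that a subject leaves the risk set at discontinuation.
- Beside these results, show the cumulative incidence of criterion 7 discontinuation by arm.

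The cost is SAP wording and a rerun of models already programmed. The criterion-level data are already needed for 3.7.3.1.3. The drawbacks are fewer events, a wider interval, and withdrawal treated as censoring, which is why the incidence display belongs alongside.
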